5.3 Agent Administration

Daratumumab 16 mg/kg will be administered per the Table 5.3.1. Participants should be observed for 30 minutes after the completion of the infusion.

Table 5.3.1. Daratumumab infusion instructions

	Dilution volume	Initial rate (first hour)	Rate increment	Maximum rate
First infusion	1000 mL	50mL/hour	50 mL/hour every hour	200 mL/hour
Second infusion^a	500 mL	50 mL/hour	50 mL/hour every hour	200 mL/hour
Subsequent infusions^b	500 mL	100 mL/hour	50 mL/hour every hour	200 mL/hour

^a Escalate only if there were no Grade 1 (mild) or greater infusion reactions during the first 3 hour of the first infusion.

^b Escalate only if there were no Grade 1 (mild) or greater infusion reactions during a final infusion rate of $\geq 100 \text{ mL/hr}$ in the first two infusions.

Vital signs (blood pressure, temperature, heart rate, respiratory rate) will be obtained before infusion, every 60 minutes (± 10 minutes) during the infusion period, and at 30 minutes (± 5 minutes) after the completion of infusion.

5.3.1 Infusion Related Reactions

For infusion reactions of any grade/severity, immediately interrupt the daratumumab infusion and manage symptoms. Management of infusion reactions may further require reduction in the rate of infusion, or treatment discontinuation of daratumumab as outlined below:

- Grade 1-2 (mild to moderate): Once reaction symptoms resolve, resume the infusion at no more than half the rate at which the reaction occurred. If the patient does not experience any further reaction symptoms, infusion rate escalation may resume at increments and intervals as appropriate (Table 5.3.1).

- Grade 3 (severe): If the intensity of the reaction decreases to Grade 2 or lower, consider restarting the infusion at no more than half the rate at which the reaction occurred. If the patient does not experience additional symptoms, resume infusion rate escalation at increments and intervals as outlined in Table 5.3.1. Repeat the procedure above in the event of recurrence of Grade 3 symptoms. Permanently discontinue daratumumab upon the third occurrence of a Grade 3 or greater infusion reaction.
- Grade 4 (life threatening): Permanently discontinue daratumumab treatment

Product description and storage information is described in Section 8.

5.4 General Concomitant Medication and Supportive Care Guidelines

Participants will be instructed not to take any additional medications (including over-the-counter products) during the course of the study without prior consultation with the investigator. At each visit, the investigator will ask the participant about any new medications he/she is or has taken after the start of the study drug.

5.4.1 Prophylactically Prescribed Medication

All prophylactic premedication administration is mandatory. An antiviral should be prescribed for herpes zoster prophylaxis, with the participant initiating treatment within one week prior to starting Daratumumab and continuing for 3 months after treatment ends.

Premedications¹:	1st & 2nd Daratumumab Infusion	3rd & Subsequent Infusions*
60 minutes before daratumumab infusion	1. Acetaminophen 975mg PO 2. Diphenhydramine 25-50mg IV or PO 3. Methylprednisolone 100mg IV 4. Famotidine 20 mg IV 5. Montelukast 10mg PO 6. Fexofenadine 60mg PO	1. Acetaminophen 975mg PO 2. Diphenhydramine 25-50mg IV or PO 3. Methylprednisolone 60mg IV
2 hours after start of the infusion (Daratumumab infusion to be paused at this point)	1. Methylprednisolone 40mg IV 2. Famotidine 20mg IV 3. Diphenhydramine 25 mg IV	n/a
Post infusion	1. Methylprednisolone 20mg PO 24 & 48 hours after infusion completion 2. Albuterol Nebulizer solution 2.5mg Q6hours PRN wheezing**	1. Methylprednisolone 20mg PO 24 & 48 hours after infusion completion 2. Albuterol Nebulizer solution 2.5mg Q6hours PRN wheezing **

*If patient has not experienced any infusion reaction. Otherwise, continue with the 1st and 2nd infusion premedication schedule until 2 consecutive infusions given without infusion reaction

** The Albuterol Nebulizer is only for patients with a higher risk of respiratory complications. It can be administered for the first 4 infusions and after that, if there is no reaction, it can be discontinued.

¹Sites outside DF/HCC may follow their internal standard practice for daratumumab premedications.

Methylprednisolone may be dose reduced per investigator discretion for participants who cannot tolerate the higher dose. Post infusion methylprednisolone may be discontinued per investigator discretion.

5.4.2 Permitted Treatments

Subjects may receive DVT prophylaxis (if needed) with LMWH, warfarin, or similar. All anticoagulants, and/or aspirin should be held in case the platelet count is <50,000 mm³.

The following medications and supportive therapies are examples of support therapies that may be used during the study:

- Colony stimulating factors, erythropoietin, and transfusion of platelets and red cells;
- It is important to prevent constipation (eg, adequate hydration, high-fiber diet, and stool softeners if needed);
- Plasmapheresis to prevent and/or treat IgM flare and symptomatic hyperviscosity

5.4.3 Avoidance of Medications

- Subjects taking oral or parenteral corticosteroids should be tapered off this medication for 5 half-lives prior to the first dose of daratumumab and must remain discontinued from all oral and parenteral corticosteroids while participating in the study (unless used for treatment of infusion reactions, rash, antiemetic prophylaxis or as part of the protocol chemotherapy regimen or subjects on low-dose corticosteroids (≤ 20 mg prednisone or equivalent) for chronic conditions. Investigators should discuss individual cases with the medical monitor.

5.5 Criteria for Taking a Participant Off Protocol Therapy

Duration of therapy will depend on individual response, evidence of disease progression and tolerance. In the absence of treatment delays due to adverse event(s), treatment may continue for 18 cycles or until one of the following criteria applies:

- Disease progression.
- Intercurrent illness that prevents further administration of treatment.
- Unacceptable adverse event(s).
- Participant demonstrates an inability or unwillingness to comply with the oral medication regimen and/or documentation requirements.
- Participant decides to withdraw from the protocol therapy.

- General or specific changes in the participant's condition render the participant unacceptable for further treatment in the judgment of the treating investigator.

Participants will be removed from the protocol therapy when any of these criteria apply. The reason for removal from protocol therapy, and the date the participant was removed, must be documented in the case report form (CRF). Alternative care options will be discussed with the participant.

In the event of unusual or life-threatening complications, treating investigators must immediately notify the PI, [name] at [contact].

5.6 Duration of Follow Up

Participants will be followed for up to 24 months after discontinuation from protocol therapy or start of new therapy or until death, whichever occurs first. Participants removed from protocol therapy for unacceptable adverse event(s) will be followed until resolution or stabilization of the adverse event.

5.7 Criteria for Taking a Participant Off Study

Participants will be removed from study when any of the following criteria apply:

- Lost to follow-up
- Withdrawal of consent for data submission
- Death

The reason for taking a participant off study, and the date the participant was removed, must be documented in the case report form (CRF).

For Decentralized Subject Registrations, the research team updates the relevant Off Treatment/Off Study information in OnCore.

6. DOSING DELAYS/DOSE MODIFICATIONS

Dose delays will be made as indicated in the following table(s). No dose modification will be allowed. The descriptions and grading scales found in the revised NCI Common Terminology Criteria for Adverse Events (CTCAE) version 4.0 will be utilized for dose delays and. A copy of the CTCAE version 4.0 can be downloaded from the CTEP website

http://ctep.cancer.gov/protocolDevelopment/electronic_applications/ctc.htm

If possible, symptoms should be managed symptomatically. In the case of toxicity, appropriate medical treatment should be used (including anti-emetics, anti-diarrheals, etc.). All adverse events experienced by participants will be collected from the time of the first dose of study treatment, through the study and until the final study visit. Participants continuing to experience toxicity at the off study visit may be contacted for additional assessments until the toxicity has resolved or is deemed irreversible.

For patients who are unable to tolerate the protocol-specified dosing schedule, dose adjustments are permitted. If administration of daratumumab must be interrupted because of unacceptable toxicity, drug dosing will be interrupted or missed according to rules described in below.

Dosing will be held for any of the following drug-related conditions:

- Grade 3 or higher non-hematologic toxicities with the following exceptions:
 - Grade 3 nausea or Grade 3 vomiting that responds to antiemetic treatment within 7 days,
 - Grade 3 diarrhea that responds to antidiarrheal treatment within 7 days
 - Grade 3 fatigue or asthenia that was present at baseline or that lasts for <7 days after the last administration of daratumumab
- Neutrophil count < 500/ μ L (growth factor permitted)
- Febrile neutropenia of any grade
- Platelet count < 50,000/ μ L in the presence of bleeding
- Platelet count < 25,000 μ L without bleeding

Participants can be retreated according to the following guidelines once non-hematological toxicity has resolved to \leq Grade 2, ANC \geq 500/ μ L, and/or platelets are \geq 25,000/ μ L without bleeding. If the toxicity has not resolved within 28 days, patients should discontinue treatment, unless allowed to continue by PI discretion.

Daratumumab treatment should be resumed when the toxicity has resolved to \leq Grade 2. If the daratumumab administration does not commence within the pre-specified window (+/- 3 days and at least 5 days between doses) of the scheduled administration date, then the dose will be considered a missed dose. Administration may resume at the next planned dosing date. A missed dose will not be made up. If participants require a dose delay for plasmapheresis then the dose can be given up to 1 week later. This would not be considered a missed dose. If more than 2 consecutive planned doses of daratumumab are missed due to AEs, treatment continuation should be discussed with the overall PI before resumption of therapy.

Potential for IgM flare

Abrupt increases in serum IgM levels following administration of anti-CD20 monoclonal antibodies and intravenous immunoglobulin are well recognized in WM patients (Treon et al, Ann Oncol 2004; Ghobrial et al, Cancer 2004; Yang et al, ASH 2010; Furman et al, ASH 2011). Such abrupt increases can prompt symptomatic hyperviscosity in patients with high serum IgM levels, i.e. >5,000 mg/dL and can contribute to worsening of IgM related morbidity such as cryoglobulinemia, cold agglutininemia, and demyelinating neuropathy. Plasmapheresis is therefore used to treat symptomatic IgM flares, as well as prophylax in patients with high serum IgM levels. Following plasmapheresis, serum IgM levels will return to steady state in 5 weeks. As such, WM patients who undergo plasmapheresis will be non-evaluable for response purposes within 4 weeks of last plasmapheresis. It is recommended that patients with symptomatic hyperviscosity or a pre-treatment serum IgM level >5,000 mg/dL undergo plasmapheresis before treatment with daratumumab. Treatment with daratumumab may be delayed for up to one week if plasmapheresis

is warranted. Close serial monitoring of serum IgM levels (at least weekly) is recommended for all participants during cycles 1 and 2. After cycle 2, monitoring would be per protocol on Days 1 & 15 of Cycles 3-6, and Day 1 of Cycles 7-18 unless directed otherwise by treating physician.

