5.2 Pre-Treatment Criteria

Cycle 1, Day 1 results do not need to meet eligibility parameters. Day 1 chemistry and hematology laboratories must be reviewed prior to treatment.

Participants must meet the following criteria on treatment days of all cycles:

- No grade 3 or higher non-hematologic toxicities with the following exceptions:
 - Grade 3 nausea or Grade 3 vomiting that responds to antiemetic treatment within 7 days,
 - Grade 3 diarrhea that responds to antidiarrheal treatment within 7 days
 - Grade 3 fatigue or asthenia that was present at baseline or that lasts for <7 days after the last administration of daratumumab
- Neutrophil count $\geq 500/\mu\text{L}$ (growth factor permitted, including on day of treatment)

- No Febrile neutropenia of any grade
- Platelet count $\geq 50,000/\mu\text{L}$ in the presence of bleeding (platelet transfusion permitted, including on day of treatment)
- Platelet count $\geq 25,000 \mu\text{L}$ without bleeding (platelet transfusion permitted, including on day of treatment)

Daratumumab treatment should be resumed when the toxicity has resolved to \leq Grade 2. If the daratumumab administration does not commence within the pre-specified window of the scheduled administration date, then the dose will be considered a missed dose. Administration may resume at the next planned dosing date. A missed dose will not be made up.

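### After a hold for low neutrophils or platelets, Sections 5.2 and 6 give two different tests for resuming daratumumab, and the 28-day rule is tied to neither

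*Combined protocol and SAP*

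**What the plan says.** **Section 6, hold.** A list introduced by "Dosing will be held for any of the following drug-related conditions" holds dosing for most Grade 3 or higher non-hematologic toxicities, ANC below 500/µL ("growth factor permitted"), febrile neutropenia, platelets below 50,000/µL with bleeding, and platelets below 25,000/µL without bleeding.

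**Section 6, retreatment.** "Participants can be retreated according to the following guidelines once non-hematological toxicity has resolved to" Grade 2 or lower. The same sentence then gives counts their own limits: ANC at least 500/µL, *and/or* platelets at least 25,000/µL without bleeding. The next sentence is the time limit: "If the toxicity has not resolved within 28 days, patients should discontinue treatment, unless allowed to continue by PI discretion".

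**Section 6, next paragraph.** "Daratumumab treatment should be resumed when the toxicity has resolved to" Grade 2 or lower. Nothing restricts this to non-hematological events. A dose outside the window is missed and not made up. After more than two consecutive misses due to adverse events, continuation is to be discussed with the overall PI.

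**Section 5.2.** "Participants must meet the following criteria on treatment days of all cycles": these include ANC at least 500/µL, platelets at least 25,000/µL without bleeding, and platelets at least 50,000/µL "in the presence of bleeding (platelet transfusion permitted, including on day of treatment"). The unqualified Grade 2 sentence and the missed-dose rule follow directly.

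**Grading.** Section 6 adopts CTCAE version 4.0 for dose delays. The cut-points are cited, not printed.

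**The concern.** For a patient held for a low count, the documents give two tests of recovery. One is an absolute count. The other is a toxicity grade, in a sentence that names no type of toxicity. Section 5.2 contains both, so it conflicts with itself as well as with the retreatment sentence in Section 6.

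A site could fairly apply a grade to a count, because the protocol does so elsewhere: Section 7.1.1.1 reports Grade 3 or 4 thrombocytopenia and neutropenia, Section 7.3.4 exempts certain Grade 4 counts from expedited reporting, and Section 7.5.3.2 lists cytopenias by grade.

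The test chosen decides whether a scheduled infusion is given or permanently lost. It may also decide whether the 28-day rule is reached. Exposure and time on treatment bear on the primary endpoint, which is best response while on therapy (Sections 11.2 and 13.5). In a multicenter study whose monitoring covers drug administration (Section 19.1), a monitor could not tell compliance from violation in the disputed range.

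**Working it through.** The plan has no figure of its own to reproduce here; the check sets the rules side by side and counts consequences.

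**1. The tests compared**

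| Event | Section 5.2 treatment-day criteria | Section 6 retreatment sentence | Unqualified sentence (5.2 and 6) |
|---|---|---|---|
| Non-hematologic | No Grade 3 or higher, with exceptions | Grade 2 or lower | Grade 2 or lower |
| ANC | ≥ 500 | ≥ 500 | Grade 2 or lower |
| Platelets, no bleeding | ≥ 25,000 | ≥ 25,000 | Grade 2 or lower |
| Platelets, bleeding | ≥ 50,000 | no branch given | Grade 2 or lower |

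**2. Where the count test and the grade test disagree**

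Let *c* be the count threshold (500 or 25,000, from Sections 5.2 and 6) and *g* the lowest count still graded 2. Since *g* is not printed, it is an assumption. The tests disagree when *c* ≤ count < *g*.

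| Count | Assumed *g* | Disputed band |
|---|---|---|
| ANC | 500 | none |
| ANC | 750 | 500–749 |
| ANC | 1,000 | 500–999 |
| Platelets, no bleeding | 25,000 | none |
| Platelets, no bleeding | 37,500 | 25,000–37,499 |
| Platelets, no bleeding | 50,000 | 25,000–49,999 |

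The tests agree only if *g* equals *c*; any higher floor opens a band.

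**3. Doses at stake**

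Take a hold that starts on a dosing day (day 0) and stays within one phase. Planned doses on days 0 to 27 number 28 ÷ dosing interval. The third consecutive miss, which triggers discussion with the overall PI, falls on day 2 × interval.

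| Phase | Interval (days) | Planned doses in days 0–27 | Third consecutive miss |
|---|---|---|---|
| Induction | 7 | 28/7 = 4 | day 14 |
| Consolidation | 14 | 28/14 = 2 | day 28 |
| Maintenance | 28 | 28/28 = 1 | day 56 |

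**4. An illustrative patient**

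Suppose ANC is 400 on Cycle 1 Day 8, then 700 on Cycle 1 Days 15 and 22 and Cycle 2 Days 1 and 8. The Day 8 dose is lost on either test.
- Count test: 700 ≥ 500, so all four later doses can be given.
- Grade test with an assumed floor of 750 or 1,000: 700 is below the floor, so none of the four is given. By Cycle 2 Day 8, 1 + 4 = 5 of the 8 induction infusions are missed.
- On the grade test, PI discussion is triggered at Cycle 1 Day 22 (day 14 of the hold). Day 28 falls on Cycle 2 Day 8. Whether the 28-day rule then applies depends on which meaning of resolved is used.

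The example assumes that growth factor, which is permitted, does not lift the count above the floor.

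**5. Platelets with bleeding**

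Suppose a patient is held at 45,000 with bleeding and recovers to 60,000 while still bleeding. Section 5.2 accepts this (60,000 ≥ 50,000) and the Section 6 hold list no longer applies. The Section 6 retreatment sentence has only a without-bleeding branch, so it does not clear the patient. This part needs no grading table.

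**6. How many patients**

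Only patients who first fall below a hold limit are involved. Section 7.1.1.1 gives Grade 3 or 4 thrombocytopenia in 14% and neutropenia in 12% of earlier monotherapy subjects, with no Grade 4 split and no count distribution. The number affected among 30 patients cannot be obtained from these figures.

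**The case against.** The best defence is that the Grade 2 sentence was meant for non-hematologic events. Both sections state non-hematologic limits as grades and neutrophil and platelet limits as counts, the Section 6 retreatment sentence makes that split explicit, and the counts in Section 5.2 match it. This is a plausible reading of intent, and it shows that the conflict comes from one general sentence set against specific count rules. The sentence does not carry the restriction, however, and it stands directly after the count criteria in Section 5.2.

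Four further objections stand in whole or part:
- A reader might infer that Sections 5.2 and 6 allow resumption *only* at Grade 2 or lower. Neither uses that word, and the treatment-day criteria in Section 5.2 accept the lower counts.
- A reader might infer that a patient is permanently stopped depending on the section consulted. That needs resolved in the 28-day rule to mean Grade 2 or lower, and the PI not to use the stated discretion. The rule follows the count-based sentence, so counts are at least as natural a reading.
- Safeguards exist: PI discussion after more than two consecutive misses, growth factor (Sections 5.2, 5.4.2 and 6) and platelet transfusion (Sections 5.2 and 5.4.2). Silence on transfusion in the Section 6 retreatment sentence is not a conflict.
- The bleeding mismatch is an omitted branch rather than an outright contradiction, because the Section 6 hold list uses the same 50,000 limit as Section 5.2.

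**Conclusion.** The point holds as an internal inconsistency that should be corrected. Two stated tests can give different dosing for the same held patient, and Section 5.2 contains both. The conflict has practical effect if the CTCAE 4.0 Grade 2 floor lies above 500 for ANC or above 25,000 for platelets. That is an assumption on these documents, with the range shown. The missing bleeding branch, the ambiguous *and/or*, and the lack of a definition of resolved for the 28-day rule do not depend on it.

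The number affected is unknown, and two tempting estimates should not be used:
- Multiplying 14% and 12% by 30 (4.2 and 3.6 patients) counts Grade 3 and 4 together and does not identify patients who crossed a hold limit.
- Entering at the eligibility limits (Section 3.1.8: ANC 1,000, platelets 50,000) does not put a patient in dispute with any fall. Without bleeding, a hold needs a fall of more than half (1,000 to below 500, or 50,000 to below 25,000).

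The effect on the response rate is plausible, through lost exposure, but it cannot be quantified from the documents.

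**What to change.** Reconcile Sections 5.2 and 6 into one resumption rule, stated once and cross-referenced from the other section. It should:
- say separately for non-hematological toxicity, ANC, platelets without bleeding and platelets with bleeding when the event counts as resolved;
- replace *and/or* with wording that shows which conditions must hold together;
- use that same definition of resolved in the 28-day rule;
- remove the duplicated Grade 2 sentence.

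The choice of threshold is for the sponsor and investigators. The cost is a few sentences in an amendment. No tests are added, because the study calendar in Section 10 already has a blood count on every infusion day.

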11. MEASUREMENT OF EFFECT

11.1 Definitions

Evaluable for toxicity: All participants who receive at least one dose of study treatment will be evaluable for toxicity from the time of their first treatment.

Evaluable for objective response: Only those participants who have measurable disease present at baseline, have received at least one cycle of therapy, and have had their disease re-evaluated will be considered evaluable for response. Response will be assessed on Day 1 of each cycle starting with Cycle 2 unless the participant has undergone plasmapheresis within the previous 4 weeks. Participants discontinuing BTK inhibitors might not be evaluable for response due to IgM rebound until Cycle 4 Day 1 (Gustine JN, et al. Ibrutinib discontinuation in Waldenstrom macroglobulinemia. *Am J Hematol* 2018; 93:511-517). These participants will have their response classified according to the definitions stated below. (Note: Participants who exhibit objective disease progression or die prior to the end of cycle 1 will also be considered evaluable.)

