11.2 Response Criteria

Complete Response (CR): A complete response (CR) is defined as having resolution of WM related symptoms, normalization of serum IgM levels with complete disappearance of IgM paraprotein by immunofixation, and resolution of any adenopathy or splenomegaly. A complete response requires reconfirmation demonstrating normal serum IgM levels, and absence of IgM paraprotein by immunofixation by a measurement repeated at least 2 weeks later.

Very Good Partial Response (VGPR): is defined as $\geq 90\%$ reduction in serum IgM levels, or normalization of serum IgM levels.

Partial Response (PR): Partial response (PR) is defined as achieving a $\geq 50\%$ reduction in serum IgM levels.

Minor Response (MR): A minor response (MR) is defined 25-49% reduction in serum IgM levels.

Progressive Disease (PD): Progressive disease (PD) is defined as occurring when a greater than 25% increase in serum IgM level occurs with an absolute increase of at least 500 mg/dL from the lowest attained response value, or progression of clinically significant disease related symptom(s). Reconfirmation of the initial IgM increase is required when IgM is the sole criterion for progressive disease confirmation. Death from any cause or initiation of a new anti-neoplastic therapy will also be considered a progression event. An increase of 1 cm in any axis for adenopathy, or 2 cm in the craniocaudal axis of the spleen will be considered evidence of progression of extramedullary disease. Development of Bing Neel syndrome, or other extramedullary disease manifestations, as well as disease transformation will be considered as progressive events.

Stable Disease (SD): Stable disease is defined as having $< 25\%$ change in serum IgM levels, in

the absence of new or increasing adenopathy or splenomegaly and/or other progressive signs or symptoms of WM.

Overall Response Rate (ORR): Includes patients who achieved MR, PR, VGPR and CR. The best overall response rate will be at any point on therapy.

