13.7.2 Evaluation of the Primary Efficacy Endpoint

All participants included in the study must be assessed for response to treatment, even if there are major protocol treatment deviations or if they are ineligible. Each participant should be assigned a response category based on the response criteria in Section 9.1.2. According to section 11.1.2, patients who underwent plasmapheresis less than 4 weeks prior to response assessment will be deemed non-evaluable, according to Section 11.1.2.

All participants who met the eligibility criteria and were enrolled in the trial will be included in the main analysis of the response rate. All conclusions will be based on all eligible participants.

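### The 4-week post-plasmapheresis exclusion contradicts the protocol's own 5-week IgM recovery time, and no reference IgM is named, so a response can be misread in either direction

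*Combined protocol and SAP*

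**What the plan says.** Section 6 (IgM flare) gives the premise and the rule in adjacent sentences. It says "Following plasmapheresis, serum IgM levels will return to steady state in 5 weeks. As such, WM patients who undergo plasmapheresis will be non-evaluable" and completes the rule as "non-evaluable for response purposes within 4 weeks of last plasmapheresis". Section 11.1 starts response assessment at Cycle 2 Day 1 and repeats it on Day 1 of each cycle, "unless the participant has undergone plasmapheresis within the previous 4 weeks". Section 13.7.2 says "patients who underwent plasmapheresis less than 4 weeks prior to response assessment will be deemed non-evaluable".

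Plasmapheresis is foreseen before treatment for symptomatic hyperviscosity or IgM above 5,000 mg/dL (Section 3.1.5) and is permitted on study (Section 5.4.2). Section 6 adds: "Treatment with daratumumab may be delayed for up to one week if plasmapheresis" is warranted.

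On response, Section 11.2 says "A minor response (MR) is defined 25-49% reduction in serum IgM levels". It does not say from which value the reduction is measured. Section 13.5 counts any fall of at least 25% during therapy as a response, also without naming the reference. Complete response must be reconfirmed, and for progression "Reconfirmation of the initial IgM increase is required when IgM is the sole criterion for progressive disease confirmation". No repeat is stated for a minor response.

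**The concern.** The 4-week rule is presented as following from the 5-week recovery, yet it releases readings a week before the protocol says IgM has settled. No section explains the missing week. The sections also differ on the boundary: Sections 6 and 11.1 can be read as excluding day 28, while Section 13.7.2 lets it count.

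The readings in question feed the primary endpoint. Best response is taken over all of therapy, so one unconfirmed Day 1 value can classify a participant as a responder for good, even if no later visit reaches 25%. The first scheduled assessment can easily fall in the gap, because cycles last 28 days and plasmapheresis may come shortly before Cycle 1 Day 1.

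The missing reference matters as much. Screening and Cycle 1 Day 1 draws can fall on either side of a plasmapheresis, and the Section 10 calendar allows the second draw to be skipped when screening was within 14 days. Whether an IgM reading after plasmapheresis looks too low or too high depends on which draw is used.

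**Working it through.** **Timing.** The gap is 35 - 28 = 7 days, that is days 28 to 34 after the last plasmapheresis (day 28 being the disputed boundary). Let s be the days from the last plasmapheresis to Cycle 1 Day 1. Cycle 2 Day 1 is nominally 28 days later (Section 5.1), so 28 ≤ s + 28 ≤ 34 gives s = 0 to 6. With the ±3-day visit window, s = 3 to 9 at a 25-day interval and s = 0 to 3 at 31 days. No section fixes s. The same example does not carry over to Cycle 2 Day 1-Cycle 3 Day 1 (21 + 14 = 35 or 28 + 14 = 42 days) or to Cycle 6 Day 1-Cycle 7 Day 1 (14 + 28 = 42 days).

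**Assumptions, none from the documents.** Plasmapheresis removes a fraction f = 0.30 to 0.70 of IgM. The share of the deficit left at day d is R(d) = 1 - d/35 (linear), 0.05^(d/35) (95% recovered at day 35) or 0.01^(d/35) (99% recovered). The depression is e(d) = f × R(d).

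**Pre-plasmapheresis reference.** A true fall t reads as 25% when (1 - t)(1 - e) = 0.75, so t = 1 - 0.75/(1 - e).

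| Day | Linear: R; t | 95% curve: R; t | 99% curve: R; t |
|---|---|---|---|
| 28 | 0.200; 12.8-20.2% | 0.091; 19.9-22.9% | 0.025; 23.7-24.4% |
| 34 | 0.029; 23.5-24.4% | 0.054; 22.0-23.8% | 0.011; 24.4-24.7% |
| 35 | 0; 25.0% | 0.050; 22.3-23.9% | 0.010; 24.5-24.8% |

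At day 28, e is 6.0-14.0%, 2.7-6.4% and 0.8-1.8% for the three curves. Example: f = 0.70, linear, day 28 gives e = 0.14 and t = 1 - 0.75/0.86 = 12.8%. Moving from day 28 to day 35 gains 1.0 to 2.4 points under the 95% curve and 0.3 to 0.8 under the 99% curve.

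**Post-plasmapheresis reference (Cycle 1 Day 1 draw), s = 1 to 6.** With no drug effect, IgM at Cycle 2 Day 1 relative to the reference is k = (1 - e(s + 28))/(1 - e(s)). The true fall needed to read as 25% is 1 - 0.75/k.

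- Largest: f = 0.70, linear, s = 1. Reference 1 - 0.7 × 34/35 = 0.32; Cycle 2 Day 1 value 1 - 0.7 × 6/35 = 0.88; k = 2.75, so 175% above the reference. Fall needed: 1 - 0.75/2.75 = 72.7%.
- Smallest: f = 0.30, 99% curve, s = 6. Reference 1 - 0.3 × 0.454 = 0.864; Cycle 2 Day 1 value 1 - 0.3 × 0.0114 = 0.997; k = 1.154, so 15% above. Fall needed: 1 - 0.75/1.154 = 35.0%.

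Waiting longer does not help here. In the first case, after full recovery k = 1/0.32 = 3.125 and the fall needed is 1 - 0.75 × 0.32 = 76%.

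**What one participant weighs.** One of 30 is 3.3 points of ORR. The rule of at least 18 of 30 (Section 13.1) has exact P(X ≥ 18) = 0.021 at ORR 40% and 0.916 at 70%, consistent with the stated 92% power and, doubled (0.042), the 4% two-sided error. One certain false responder means that 17 true responses suffice: P(X ≥ 17 at 40%) = 0.048. One certain missed responder means that 19 are needed: P(X ≥ 19 at 70%) = 0.916 - P(X = 18) = 0.916 - 0.075 = 0.841. These are illustrations, not forecasts.

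**The case against.** A fair defence is that the operative rule is consistent: all three sections apply 4 weeks, so sites and analysts have one rule apart from the boundary day, and the 5-week sentence is only background. That stands as far as conduct goes. But the text offers the 5 weeks as the reason for the rule, and the rule does not follow from it.

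The reach is also narrow. With a pre-plasmapheresis reference it takes plasmapheresis, a Day 1 visit in a 7-day slot, a near-threshold fall, and no genuine 25% fall at any later visit. There is partial protection too: "Participants discontinuing BTK inhibitors might not be evaluable for response due to IgM rebound until Cycle 4 Day 1". All of this stands, and limits the size of the problem. The protection covers only participants stopping those drugs, and only as a possibility.

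A reader might infer that the gap inflates the ORR. The documents do not support that, because the direction turns on a reference they do not state. Section 1.1 adopts the Sixth Workshop criteria by citation, and whether those fix a reference after plasmapheresis cannot be checked here. Nor does residual plasmapheresis effect create a minor response by itself: the largest assumed depression at day 28 is 14%, short of 25%. The 12.8% figure is a corner case that needs 70% removal, linear recovery and a reading on the disputed day 28; at day 29 the same extreme is 14.8%. Finally, a 35-day window alone gains little under the exponential curves.

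**Conclusion.** The mismatch between 5 and 4 weeks is certain from the text and should be fixed. On the protocol's own premise, an unsettled IgM can set an unconfirmed best response in the primary endpoint.

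The size is conditional on the assumed 30-70% removal and the three assumed recovery curves. With a pre-plasmapheresis reference, a true fall of 12.8-24.4% reads as 25% at day 28, and of 22.0-24.7% at day 34: false response among near-threshold participants. With a post-plasmapheresis reference the error is false non-response and larger, with a true fall of about 35-73% needed (s = 1 to 6). The undefined reference is therefore at least as important as the missing week. The documents give neither the number of participants having plasmapheresis nor its timing, so no net bias in ORR can be stated in either direction.

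**What to change.** 1. Reconcile Sections 6, 11.1 and 13.7.2. On the protocol's own premise, use one 35-day window for the response analysis and state whether the boundary day counts. If 4 weeks is intended, correct and justify the 5-week statement instead. Section 13.7.2 also points to a Section 11.1.2 that does not exist; it should cite Section 11.1.
2. With equal priority, add a sentence to Section 11.2 naming one reference IgM for participants who have plasmapheresis, and make sure the calendar obtains that draw. The window alone does not correct the error from a post-plasmapheresis reference.
3. Add a sensitivity analysis of ORR that does not count responses seen only within 5 weeks of plasmapheresis.

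Keep these participants in the Full Analysis Set denominator of Section 13.5.

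The cost is a few wording changes and one extra table. The sample size and the decision rule stay as they are. Some participants lose one Day 1 assessment; in the example Cycle 2 Day 1 is lost and Cycle 3 Day 1 becomes the first. Repeated plasmapheresis restarts the window, and a participant who stops very early could lose the only assessment and count as a non-responder. None of this changes when plasmapheresis or study drug is given.
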